STUDY DESIGN General This open-label extension study will evaluate the safety of long-term twice-monthly administration of somavaratan in adults with GHD. This is an open-label, multicenter study open to subjects completing a Versartis adult GHD study as well as approximately 40 new somavaratan naïve subjects (either rhGH treatment naïve or currently receiving daily rhGH therapy). All subjects will receive twice-monthly (every 15 days \pm 2 days) subcutaneous (SC) somavaratan. Doses will be titrated to each subject's individual IGF-I responses based on the IGF-I level 7 days post-dose until a maintenance dose is achieved. Maintenance dose is defined as an IGF-I value between 0 and 2.0 SDS for two consecutive 7 day post-dose time points (Day 8, peak level). Subjects receiving somavaratan once-monthly in this study (Protocol 15VR8) or in a previous somavaratan study (Protocol 15VR7), will have their dose decreased by half (minimum dose of 20 mg, 40 mg for women on estrogen, rounded down to the nearest even number) and will be titrated per the Dose Titration Plan (Table 2). New subjects enrolling in this study will be assigned to one of two cohorts and will receive a starting dose of 20 mg twice-monthly (40 mg for women on estrogen) (Table 1) and will be

titrated per the Dose Titration Plan (Table 2). Maintenance doses may be adjusted further based on PD data at the discretion of the Investigator or Medical Monitor.

Table 1 Study Drug Starting Dose Information:

Subject Cohort Assignment	Fixed Starting Study Dose	Frequency of Administration
Cohort 1: Adults with GHD irrespective of age and gender	20 mg	Twice-Monthly
Cohort 2: Women receiving oral estrogens	40 mg	Twice-Monthly

Table 2 Dose Titration Plan

Downward Dose Titration		
IGF-I at Day 8	Cohort 1	Cohort 2
0 to 2.0 SDS	No change in dosing	No change in dosing
2.01 to 3.0 SDS	4 mg dose decrement	4 mg dose decrement
Greater than 3.0 SDS	10 mg dose decrement	10 mg dose decrement
Upward Dose Titration ¹		
IGF-I at Day 8	Cohort 1	Cohort 2
-1.0 to 0 SDS	4 mg dose increment	10 mg dose increment
Less than -1.0 to -2.0 SDS	10 mg dose increment	20 mg dose increment
Less than -2.0 SDS	20 mg dose increment	40 mg dose increment

1: Maximum allowable dose is 250.0 mg

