Despite dose adjustments (reductions), of the 29 subjects that completed 5 doses in the Phase 2 study at the time of this protocol amendment, IGF-I values 7 days after the last (fifth) dose were > 2.0 SDS in 16 subjects (55%) and > 3.0 SDS in 7 subjects (24%).

Based on these findings, it was determined that:

- A lower starting dose is needed
- The maintenance doses in rollover subjects seems to be too high, and a lower maintenance dose is needed
- The dose titration plan was not adequate to address the high IGF-I levels at Day 8 and a new titration plan based solely on IGF-I SDS 7 days after dosing is proposed
- The dosing frequency should be revised to twice-monthly to allow for adequate response during the dosing interval with reduced IGF-I excursions above 2.0 SDS
- Dosing initiation and titration should be made on a fixed (mg) basis and not be based upon-body weight adjusted (mg/kg) basis

Starting Dose

Evaluation of the doses resulting in Day 8 IGF-I above and below 2.0 SDS indicate that for adult subjects with GHD (except women receiving estrogens), 20 mg was the lowest dose that did not result in a response > 2.0 SDS in 90% of the subjects. For women receiving estrogens, a similar analysis was performed and the identified starting dose was 40 mg.

A fixed starting dose regardless of weight, age and gender is therefore planned for this study:

- 20 mg for all subjects other than women receiving oral estrogen
- 40 mg for women receiving oral estrogen

Dosing Frequency

Data from the ongoing analysis of the Phase 2 study have shown that the pre-dose (trough) IGF-I levels were similar to the baseline IGF-I levels (prior to any somavaratan exposure), suggesting that the duration of effect was less than one month. In addition, after the last (fifth) dose of somavaratan in the Phase 2 study, IGF-I levels at 21 days after dosing had already diminished to values not different than the pre-dose levels. Based on this analysis, the planned dosing frequency for this study is:

- Twice-Monthly

Continued Dosing in Rollover Subjects Presently Participating in This Study

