As previously described, approximately 50% of the subjects who completed the 15VR7 study and rolled over to the 15VR8 protocol still have high IGF-I levels 7 days after somavaratan administration (Day 8). A lower dose is needed to prevent the transient IGF-I excursions. For rollover subjects, it is proposed that the current once monthly dose they are receiving will be divided in 2, and rounded down to the nearest even number (minimum dose 20 mg, 40 mg for women on oral estrogen) and administered twice-monthly (example: current dose is 54 mg, divided by two = 27 mg, rounded down to nearest even number = 26 mg. The subject will begin to receive somavaratan 26 mg twice-monthly).

Titration Plan

The titration plan will be modified to be based exclusively on IGF-I at Day 8, which represents the sampling point of the highest response to Somavaratan. The objective of the new titration plan is to achieve an IGF-I at Day 8 within 0 and 2.0 SDS while ensuring that the IGF-I response does not exceed 2.0 SDS.

After subjects achieve maintenance dosing (two consecutive IGF-I at Day 8 within target range under the same dose) doses may be modified based on the Investigator or Medical Monitor clinical judgment with the goal to maintain IGF-I SDS at Day 8 within target range (0 to 2.0).

Summary of the Proposed Changes to Version 2 of Protocol 15VR8

Synopsis

- Updated Objective section to include as a secondary objective to evaluate the dose (starting and maintenance) and the dose titration plan of twice-monthly somavaratan during long-term treatment
- Updated **Study Design** section to describe the twice-monthly dosing regimen, starting doses and treatment cohorts
- Updated the **Inclusion/Exclusion Criteria** to indicate that new naïve to somavaratan treatment subjects must agree to a wash out period of minimum 14 days and have a screening IGF-I SDS < 0
- Updated the **Test Product, Dose and Mode of Administration** section indicating the new dosing regimen and dose titration for all subjects based on the Day 8 IGF-I SDS. Updated the Dose Titration Plan (Table 2)

Updated Section 3.1, **Overall Study Design and Plan** to describe:

- The twice-monthly dosing regimen and starting doses that will be used for all subjects
- The visit schedule all subjects will follow
- The dosing cohorts that will be used in the study
- The Dose Titration Plan (Table 2)

Updated Section 3.7, **Inclusion Criteria**:

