3 INVESTIGATIONAL PLAN

3.1 Overall Study Design and Plan

This open-label extension study will evaluate the safety of long-term twice-monthly administration of somavaratan in adults with GHD. This study is open to subjects completing a Versartis adult GHD study as well as approximately 40 new somavaratan naïve subjects (either rhGH treatment naïve or currently receiving daily rhGH therapy). A total of up to 250 subjects may be enrolled in this study. All subjects will receive twice-monthly (every 15 days \pm 2 days) subcutaneous (SC) somavaratan. All subjects will have somavaratan doses titrated per the Dose Titration Plan (Table 2) to each subject's individual IGF-I responses based on the IGF-I level collected 7 days post-dose (Day 8) until a maintenance dose is achieved. Maintenance dose is defined as an IGF-I value between 0 and 2.0 SDS for two consecutive 7 day post-dose time points (peak).

Subjects receiving somavaratan once-monthly in this study (Protocol 15VR8) or in a previous somavaratan study (Protocol 15VR7), will have their dose decreased by half (minimum dose of 20 mg, 40 mg for women on estrogen, rounded down the nearest even number) and will be titrated per the Dose Titration Plan (Table 2).

New subjects naïve to somavaratan treatment enrolling in this study will be assigned to one of two cohorts and will receive a starting dose of 20 mg twice-monthly (40 mg for women on estrogen) (Table 1) and will be titrated per the Dose Titration Plan (Table 2).

Maintenance doses may be adjusted further at the discretion of the Investigator or Medical Monitor while maintaining IGF-I at Day 8 (7 days post dose) within target range. For patients on maintenance dose that have IGF-I levels $>$ 2.0 SDS at any point during the maintenance period, dose adjustment shall be made by the Investigator or Medical Monitor based on clinical judgment with the objective to achieve and maintain IGF-I at day 7 post-dose between 0 and 2.0 SDS. Any change in somavaratan dose in a subject that has achieved maintenance dosing will be followed by an ad-hoc Day 8 IGF-I measurement to ensure IGF-I values are within target range (0 and 2.0 SDS).

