4 STUDY TREATMENT(S)

4.1 Description of Treatment(s)

4.1.1 Somavaratan Treatment

Somavaratan will be provided either in a vial and syringe configuration or as an autoinjector device (when available) and administered as subcutaneous injection(s) in the thigh, abdomen, upper arm or buttocks. Injection sites shall be rotated. Study drug may be administered by trained subjects/caregivers, or a health care professional.

Somavaratan is formulated at a nominal concentration of 100 mg/mL in 20 mM histidine, 154 mM sodium chloride, pH 5.5. Somavaratan is a colorless, clear liquid, free from visible particles. See Section 4.2 for starting dosages.

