4.2 Treatments Administered

All subjects will receive somavaratan twice-monthly.

- Subjects receiving somavaratan once monthly in a prior Versartis adult GHD study or in this study, irrespective of the cohort assignment and whether they have achieved maintenance dosing, will transition to receive treatment at half of their current dose (rounded down to the nearest even number, minimum dose of 20 mg).
- New subjects naïve to somavaratan will be assigned to one of two treatment cohorts (Table 1) with different starting doses based on the subject's use of oral estrogens. The initial dose will be a fixed dose.

All subjects will have Day 8 IGF-I SDS evaluated each month with subsequent dose adjustments made per the Dose Titration Plan (Table 2).

Table 1 Study Drug Starting Dose Information

Subject Cohort Assignment	Fixed Starting Study Dose	Frequency of Administration
Cohort 1: Adults with GHD irrespective of age and gender	20 mg	Twice-Monthly ¹
Cohort 2: Women receiving oral estrogens	40 mg	Twice-Monthly ¹

1: Allowable dosing window is every 15 days ± 2 days

Table 2 Dose Titration Plan

Downward Dose Titration		
IGF-I at Day 8	Cohort 1	Cohort 2
0 to 2.0 SDS	No change in dosing	No change in dosing
2.01 to 3.0 SDS	4 mg dose decrement	4 mg dose decrement
Greater than 3.0 SDS	10 mg dose decrement	10 mg dose decrement
Upward Dose Titration¹		
IGF-I at Day 8	Cohort 1	Cohort 2
-1.0 to 0 SDS	4 mg dose increment	10 mg dose increment
-1.0 to -2.0 SDS	10 mg dose increment	20 mg dose increment
Less than -2.0 SDS	20 mg dose increment	40 mg dose increment

1: Maximum allowable dose is 250.0 mg

The starting doses and Dose Titration Plan (Tables 1 and 2) may be altered by the Sponsor based on continued evaluation of the Phase 2 data and/or data gathered during this study. Adjustments may be implemented to alleviate safety concerns or optimize normalization of IGF-I SDS responses. The Investigator and Medical Monitor may agree to temporarily alter or suspend a subject's dose during illness or injury.

If a subject on maintenance dose has an IGF-I value outside the target range, further dose adjustments will be considered on an individual basis by the Investigator or Medical Monitor with the objective to achieve and maintain IGF-I SDS at Day 8 within target range (IGF-I SDS between 0 - 2.0)

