4.3 Selection and Timing of Dose for Each Subject

The Medical Monitor will review results of all available medical history and Screening activities and notify the Investigator and Premier (the CRO) if the subject may be enrolled in the study.

Subjects will receive somavaratan every 15 days \pm 2 days starting on Day 1. All doses will be scheduled relative to Day 1, not relative to the prior dose. If needed, dose adjustments will occur monthly until dose stabilization is achieved. Once maintenance dose is achieved, further adjustments may be made at the discretion of the Investigator while keeping IGF-I at day 7 post-dose between 0 - 2.0 SDS.

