5 STUDY PROCEDURES

For subjects who participated in a previous somavaratan study:

- Up to 30 day Enrollment period for Inclusion/Exclusion Criteria; the Day 1 visit may occur simultaneously with the last visit of the subject's previous somavaratan study
- Subjects receiving somavaratan once monthly in a prior Versartis adult GHD study or in this study, irrespective of the cohort assignment and whether they have achieved maintenance dosing, will transition to receive treatment at half of their current dose (rounded down to the nearest even number, minimum dose of 20 mg).
- Monthly dose titration period (Table 2) with adjustments to somavaratan doses as needed
- Twice-monthly treatment with maintenance dose of somavaratan

For new subjects who are either receiving daily rhGH therapy or are treatment naive:

- Up to 30 day Screening period for Inclusion/Exclusion Criteria
 - Minimum of 14 day washout period for subjects currently receiving daily rhGH treatment
- Fixed starting dose (Table 1) with monthly dose titration period (Table 2) with adjustments to somavaratan doses as needed
- Twice-monthly treatment with maintenance dose of somavaratan

All subjects will have Day 8 IGF-I SDS evaluated each month with subsequent dose adjustments made per the Dose Titration Plan (Table 2)

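### For rollover women on oral estrogen, Sections 4.2 and 5 set a 20 mg minimum converted dose, while the synopsis, Section 3.1 and the Version 2 rationale set 40 mg.

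*Combined protocol and SAP*

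**What the plan says.** Version 2 converts all subjects on once-monthly somavaratan, whether in this study or coming from an earlier one, to twice-monthly injections at half the dose. Five places state the conversion, in two forms.

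**One minimum for everyone.**
- Section 4.2 (Treatments Administered): these subjects "will transition to receive treatment at half of their current dose (rounded down to the nearest even number, minimum dose of 20 mg"). It has no separate figure for women on estrogen.
- Section 5 (Study Procedures) repeats the rule and, like Section 4.2, applies it "irrespective of the cohort assignment and whether they have achieved maintenance dosing".

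**A higher minimum for women on estrogen.**
- Synopsis, Study Design: "minimum dose of 20 mg, 40 mg for women on estrogen, rounded down to the nearest even number".
- Section 3.1: "minimum dose of 20 mg, 40 mg for women on estrogen, rounded down the nearest even number".
- Version 2 rationale, on continued dosing in rollover subjects: "minimum dose 20 mg, 40 mg for women on oral estrogen".

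Section 4.1.1 directs the reader to the first form: "See Section 4.2 for starting dosages". The starting-dose part of the rationale explains where 40 mg comes from: "For women receiving estrogens, a similar analysis was performed and the identified starting dose was 40 mg".

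**The concern.** A protocol should give one first converted dose for a given subject. Here, a site working from Section 4.2 and a site working from Section 3.1 can each follow the text correctly and give the same woman different doses. The supplied text has no rule saying which section takes precedence, and the one cross-reference on starting dosages leads to the section without the 40 mg figure. Revising the dose of rollover subjects is also a stated purpose of Version 2.

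Two things are at stake. The first is the dose actually given. Under Table 2 a Day 8 IGF-I of 0 to 2.0 SDS means no change, and two consecutive such values define the maintenance dose. The converted dose can therefore become the long-term dose. The second is interpretation. Evaluating the starting dose, maintenance dose and titration plan is a secondary objective, and Section 8.1 presents all summaries by cohort. Cohort 2 could contain women converted under different rules, with nothing in the plan to tell them apart.

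**Working it through.** **Inputs**
- Conversion: half the once-monthly dose, rounded down to an even number of mg (Sections 3.1, 4.2 and 5, synopsis, rationale).
- Minimum *m*: 20 mg (Sections 4.2 and 5), or 40 mg for women on estrogen (synopsis, Section 3.1, rationale).
- Titration steps for Cohort 2: Table 2.

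**Formula.** For a once-monthly dose *D* in whole mg,

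converted dose = max(*m*, 2 × floor(*D*/4)).

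**The protocol's example.** The rationale takes *D* = 54: 54/2 = 27, rounded down to 26 mg. The formula with *m* = 20 gives max(20, 2 × 13) = 26 mg, so the example is reproduced. With *m* = 40, the rule for a woman on oral estrogen, the same dose gives max(40, 26) = 40 mg.

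**The two rules compared**

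| Once-monthly dose (mg) | 20 mg minimum | 40 mg minimum | Ratio |
|---|---|---|---|
| 43 or less | 20 | 40 | 2.00 |
| 44 | 22 | 40 | 1.82 |
| 48 | 24 | 40 | 1.67 |
| 54 | 26 | 40 | 1.54 |
| 60 | 30 | 40 | 1.33 |
| 70 | 34 | 40 | 1.18 |
| 76 to 79 | 38 | 40 | 1.05 |
| 80 | 40 | 40 | 1.00 |
| 100 | 50 | 50 | 1.00 |

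The rules differ at every dose below 80 mg and agree from 80 mg upward. The largest gap is 20 mg per injection.

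**Are such doses plausible?** Phase 2 starting doses were 0.6 to 1.0 mg/kg (rationale). Assuming a body weight of 60 to 80 kg, that is 0.6 × 60 = 36 mg to 1.0 × 80 = 80 mg before titration. Nearly all of that range lies where the rules differ. Individual doses after titration are not given.

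**Does titration remove the gap?** Section 4.3 says: "If needed, dose adjustments will occur monthly until dose stabilization is achieved". The number of monthly steps needed is ceil(gap/step).

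| Gap | Up, 10 mg steps | Up, 20 mg steps | Down, 10 mg steps | Down, 4 mg steps |
|---|---|---|---|---|
| 20 mg (20 against 40) | 2 | 1 | 2 | 5 |
| 14 mg (26 against 40) | 2 | 1 | 2 | 4 |

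A 40 mg increment closes either gap in one step but overshoots (20 to 60 mg, or 26 to 66 mg). These counts are illustrative, since they assume that IGF-I stays in the same Table 2 band after each change. If Day 8 IGF-I is already within 0 to 2.0 SDS, Table 2 requires no step and the gap remains.

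**Does Table 1 settle it?** No. Table 1 gives Cohort 2 a 40 mg dose, but Section 4.2 ties that table to new subjects naïve to somavaratan and gives converting subjects a separate bullet.

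**The case against.** The strongest reply is that this is a drafting slip and not two dosing policies. The phrase about cohort assignment sits beside the one about maintenance status. Its natural job is to say that everyone's dose is halved, and the minimum comes later, in a parenthesis. An exception stated in three places was probably just left out of the other two. That reading is reasonable. It explains how the conflict arose but does not remove it: Sections 4.2 and 5 still give a single 20 mg minimum, do not defer to an exception elsewhere, and need the same correction.

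The other points concern weight, and much of them stands:
- **Safety.** Where the rules differ, both doses are at or below the Cohort 2 starting dose. IGF-I is sampled on Days 1, 8, 16 and 23 of Month 1. A woman who stays on her converted dose does so because her IGF-I is on target.
- **Analysis.** Rollover doses are individual by design, so first converted doses vary under either rule. Summaries are descriptive with no hypothesis tests, and doses given are recorded. The effect on Cohort 2 summaries is modest.
- **Numbers.** No document shows a rollover woman on oral estrogen taking less than 80 mg once monthly, and the two-fold gap needs a dose below 44 mg. The number affected could be zero.

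The rationale does not make the choice obvious. It gives 40 mg as the starting dose for women on estrogen, but also says that rollover doses seem too high. The sponsor should decide, not the site.

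**Conclusion.** The concern holds. Current sections give incompatible minimum doses for the same subjects, and following one breaches another. For a woman on oral estrogen the first twice-monthly dose is ambiguous at every once-monthly dose below 80 mg, by up to 20 mg per injection, or two-fold. At the protocol's example dose it is 26 or 40 mg.

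This is an internal inconsistency that should be corrected. It is not a safety finding, and it does not threaten the primary objective. The conclusion rests on the plain text and on whole-mg arithmetic. Only the plausibility range uses an assumption, a body weight of 60 to 80 kg. The number of women affected cannot be stated from the documents.

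**What to change.** 1. Choose the minimum. If 40 mg is intended, amend the parenthesis in Sections 4.2 and 5 to give 20 mg, or 40 mg for women receiving oral estrogen. That matches the rationale and Table 1. If 20 mg is intended for all, remove the 40 mg exception from the synopsis and Section 3.1, and correct the rationale to agree.
2. Say oral estrogen throughout. The synopsis and Section 3.1 currently say estrogen without the route, whereas Cohort 2 is defined by oral use.
3. For Cohort 2 subjects already converted, derive a flag for the minimum applied and show it in the dose summaries.

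The cost is a protocol clarification of one parenthesis in two sections, plus one variable derived from the administered doses entered in the IWRS (Section 4.9.1). No extra subjects, visits or samples are needed.

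A separate tidy-up can go in the same amendment. In Section 4.2, Table 2 places an IGF-I of exactly -1.0 SDS in two rows. The synopsis version of the table avoids this and should be used in both places.

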4.3 Selection and Timing of Dose for Each Subject

The Medical Monitor will review results of all available medical history and Screening activities and notify the Investigator and Premier (the CRO) if the subject may be enrolled in the study.

Subjects will receive somavaratan every 15 days \pm 2 days starting on Day 1. All doses will be scheduled relative to Day 1, not relative to the prior dose. If needed, dose adjustments will occur monthly until dose stabilization is achieved. Once maintenance dose is achieved, further adjustments may be made at the discretion of the Investigator while keeping IGF-I at day 7 post-dose between 0 - 2.0 SDS.

4.4 Method of Assigning Subjects to Treatment Groups and Subject Number Assignments

Enrollment into the study will be based on the order of appearance of subjects completing Screening activities with approval by the Medical Monitor. A unique Subject Number will be sequentially assigned to each subject. Subject numbers will not be re-assigned.

4.5 Concomitant Therapy

Restrictions on prior and concomitant therapy are provided in the Inclusion and Exclusion Criteria (Sections 3.7 and 3.8). At Screening, subjects may have completed a Versartis adult GHD study, be rhGH treatment naïve, or, if currently receiving daily rhGH injections for treatment of GHD, must undergo a minimum of a 14-day wash-out period prior to initiating study treatment (Section 6.2). Any underlying disorders associated with GHD must have been clinically stable for at least six months. For subjects taking other hormone replacement therapy, they must have been on a stable course of treatment for at least three months prior to Screening (routine dose adjustments are considered part of a stable course of treatment). Adjustments to these medications (thyroid, glucocorticoid and antidiuretic hormones) are permitted during the protocol as required by standard medical practice.

If subjects are diagnosed with adrenal insufficiency at Screening, subject must be placed on stable glucocorticoid treatment doses for at least 30 days prior to enrollment. These subjects may re-enter screening after stabilization of glucocorticoid treatment. Other prior or concomitant therapy will be reviewed and approved by the Investigator and the Medical Monitor.

